7 STUDY INTERVENTION ADMINISTRATION

- **Randomization:** The study statistician will write a computer program to perform a stratified random assignment to the initial two conditions on a 1:1 basis using a permuted block algorithm.

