MSI-R (AFC, PSC)	Marital Satisfaction Inventory-Revised (Affective Communication, Problem-Solving Communication Subscales)
EDQOL	Eating Disorders Quality of Life
CSQ	Client Satisfaction Questionnaire

PROTOCOL SYNOPSIS

Study Title	Targeting Relationship Domains in Community-Based Treatment of Binge-Eating Disorder
Funder	NIMH
Study Rationale	Clinicians' options for BED treatment are inadequate. Treatments for BED have demonstrated efficacy in controlled settings with specialist therapists and expert supervision, but much less is known about the effectiveness of BED interventions and whether the transition of evidence-based treatments to the community results in poorer outcomes. UNITE activates a key resource by incorporating an important part of the patient's social environment (the partner) into treatment. The investigators hypothesize that UNITE will show preliminary evidence of being superior to CBT-E in achieving binge abstinence via engaging ED-related relationship targets, including improved (a) communication around the disorder, (b) disorder-specific interpersonal problem-solving/ behavioral change skills, and (c) partner-assisted emotion regulation. The investigators will assess targeted relationship domains with observational and speech prosody measures during clinic interactions and self-reports reflecting experiences outside of the clinic. Because the couple is learning how to work together to address BED, the investigators hypothesize that maintenance of gains will show evidence consistent with superiority in UNITE.
Study Objective(s)	Primary 
• To compare the effectiveness of UNITE versus CBT-E in achieving abstinence from binge-eating. Secondary 
• To compare the effectiveness of UNITE versus individual CBT-E in decreasing ED-related psychopathology, depression, and anxiety.• To compare target relationship domains in patients and partners.• To compare treatment satisfaction and ED-related quality of life in UNITE versus CBT-E

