Statistical and Analytic Plan	Intent-to-treat or modified intent-to-treat, if appropriate, will comprise the primary approach. Differential treatment effects will be analyzed with multilevel mixed-effects models with fixed effects and interactions for Time, Treatment, and (where appropriate) Participant Status (i.e., patients/partners), and with random effects to address clustering.
Data and Safety Monitoring Plan	The DSMG will be responsible for data quality management and ongoing assessment of participant safety.

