2 STUDY OBJECTIVE

2.1 Primary Objective: The purpose of this study is to test the feasibility, acceptability, and preliminary effectiveness of a novel couple-based intervention for BED (UNITE) relative to an established evidence-based individual treatment (CBT-E) in a community clinic setting.

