5.3 Statistical Methods

- **Baseline Data.** Sociodemographics and baseline clinical characteristics will be summarized with descriptive statistics.
- **Efficacy Analysis.** Study hypotheses will be tested using intent-to-treat or modified intent-to-treat methods, as appropriate. For patient-only outcomes, differential treatment effects will be tested with multilevel mixed-effects models with fixed effects and two-way interactions for Time and Treatment and a random effect for Patient. For outcomes assessed in both patients and partners, differential treatment effects will be tested with multilevel mixed-effects models with fixed effects and two- and

three-way interactions for Time, Treatment, and Participant Status (i.e., Patient or Partners) and random effects for Participant and Couple. Linear, logistic, and Poisson distribution functions will be used to model outcome variables. Treatment satisfaction, assessed at post-treatment only, will be compared between patients in UNITE and CBT-E with linear regression.

- **Safety Analysis.** Adverse events will be summarized as a numerator (total affected) and denominator (number at risk) for patients and partners in each treatment arm using the ClinicalTrials.gov categories of all-cause mortality, serious adverse events, and other (not including serious) adverse events.

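### Randomisation is stratified by unnamed factors that no model includes; if those factors are prognostic, the CSQ comparison is valid but conservative (minor)

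*Combined protocol and SAP*

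**What the plan says.** Section 7 gives the whole description of the allocation: the study statistician's program will "perform a stratified random assignment to the initial two conditions on a 1:1 basis using a permuted block algorithm". No factor, level, number of strata or block size appears there or elsewhere, and nothing at that place is marked as blacked out.

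Section 5.3 lists the model terms. Patient-only outcomes get "multilevel mixed-effects models with fixed effects and two-way interactions for Time and Treatment and a random effect for Patient". Outcomes taken from both members of the couple add "three-way interactions for Time, Treatment, and Participant Status (i.e., Patient or Partners) and random effects for Participant and Couple". The synopsis agrees: "fixed effects and interactions for Time, Treatment, and (where appropriate) Participant Status". None of these terms is a stratification factor.

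The CSQ has its own analysis: "Treatment satisfaction, assessed at post-treatment only, will be compared between patients in UNITE and CBT-E with linear regression". No covariate is named. Section 4.2 and Table 3 schedule the CSQ only at the post-treatment assessment, after session 16.

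Satisfaction is a secondary objective in the synopsis ("To compare treatment satisfaction and ED-related quality of life in UNITE versus CBT-E"), and section 2.1 gives the purpose as to "test the feasibility, acceptability, and preliminary effectiveness of a novel couple-based intervention for BED".

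**The concern.** Blocking within strata balances the arms on the stratification factors. If those factors predict the outcome, the balance reduces the true sampling variance of the difference between arms, and even an unadjusted difference in means has that smaller variance. An ordinary regression on treatment alone does not know this. It counts the between-stratum variation as residual error and reports a standard error that is too large. Confidence intervals are then too wide and the test rejects less often than its nominal level.

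The CSQ is exposed because it has a single post-treatment value, so no within-patient change can remove differences between strata. At stake is precision that the design has already bought, on a secondary outcome in a trial whose section 5.4 concedes that it is not powered for every hypothesis.

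There is also a plain reporting gap: a stratified scheme with unnamed factors cannot be reproduced or checked against the randomisation program.

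**Working it through.** **Inputs from the documents.** Allocation is 1:1 in stratified permuted blocks (section 7). Enrolment is 38 couples, with 34 expected to complete (section 3.2). Each couple has one patient, so the CSQ comparison has about 34 patients; 4 of 38 (10.5%) are lost before the CSQ is given. The plan states no alpha, SD, effect size or power, so it has no figure to reproduce.

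**Assumptions, not in the documents.** Two-sided 5% test; one binary factor with equally likely levels; block size 4; four patients lost at random; strata explaining a share R² of the within-arm outcome variance; a true difference of 0 or 0.9 SD.

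**Step 1: standard error.** With within-arm SD 1 and n = 34, the unadjusted regression reports about 2/√n = 2/√34 = 0.343. Under exact balance within strata the true value is 0.343 × √(1 − R²):

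- R² 0.1: 0.343 × 0.949 = 0.325
- R² 0.2: 0.343 × 0.894 = 0.307
- R² 0.3: 0.343 × 0.837 = 0.287

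In simulation, incomplete blocks and the four losses disturb the balance a little, so the true values are slightly higher:

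| R² | Mean reported SE | True SE | Ratio |
|---|---|---|---|
| 0.1 | 0.3412 | 0.3271 | 1.04 |
| 0.2 | 0.3412 | 0.3148 | 1.08 |
| 0.3 | 0.3425 | 0.2963 | 1.16 |

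With the stratum term added, the two agree (R² 0.3: 0.2861 reported, 0.2873 true).

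**Step 2: type I error and power, 34 of 38 analysed, 20,000 simulated trials per cell.**

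| R² | Type I, unadjusted | Type I, adjusted | Power at 0.9 SD, unadjusted | Power at 0.9 SD, adjusted | Gain (points) |
|---|---|---|---|---|---|
| 0.1 | 3.9% | 4.8% | 72.4% | 75.5% | 3.1 |
| 0.2 | 3.1% | 4.9% | 73.2% | 80.6% | 7.4 |
| 0.3 | 2.5% | 5.1% | 74.7% | 86.1% | 11.4 |

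A repeat under the same settings gave unadjusted type I error of 4.3, 3.2 and 2.5% and power of 73 v 76, 73 v 81 and 75 v 86%. I therefore quote rounded figures.

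**Step 3: sensitivity.** With two or four strata, block size 2 or 4 and 34 analysed, unadjusted type I error is 3.9–4.5% at R² 0.1, 3.2–3.7% at 0.2 and 2.3–2.5% at 0.3. At a 0.8 SD difference, power rises from about 62% to 65–66%, 70–71% and 76–77%.

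**Step 4: factors with little or no prognostic value.** At R² 0.03, with all 38 analysed and 0.9 SD, power is 77.4% unadjusted and 78.1% adjusted. At R² 0 it is 77.5 v 77.4%, a cost of 0.1 point for one binary factor; with 34 analysed the cost is again about 0.1 point. More strata cost more: at 0.8 SD, four strata entered as three indicators give 61.9 v 61.0% (block size 2) and 61.9 v 60.5% (block size 4), about 1 point.

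**Step 5: the other outcomes.** A stratum effect that is constant over time cancels from a within-patient change. Simulated pre–post change in 38 patients without stratum terms has type I error of 4.7% at R² 0.3 and 5.2% at R² 0.5. For abstinence I used a single-visit logistic test with 38 patients and a treatment odds ratio of 4, comparing the two analyses at equal test size. Power is 57.9% unadjusted v 57.7% adjusted with a stratum odds ratio of 2, and 51.6 v 50.7% with 4. That is no gain.

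**The case against.** The strongest objection is that the size rests wholly on assumptions. The factors are unknown, and nothing in the documents suggests that baseline stratifiers explain 20–30% of the variation in satisfaction with therapy. This stands. The documents cannot show that any precision is lost; they show only that the analysis leaves out something the design may have used.

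Second, the section 7 sentence speaks of two initial conditions, although the trial has two arms and no later randomisation. A reader might infer that the sentence was carried over from another design and that no stratification took place. The documents neither confirm nor exclude this, so the fix must allow for it.

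Third, the CSQ is one of about 14 secondary measures in section 5.1, and no section ties acceptability to a between-arm test of it. That is fair and limits the severity.

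Fourth, linear regression does not forbid covariates. True, but the plan names none, while it lists the terms of its other models in full.

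Fifth, naming the factors might be presented as prespecification. That benefit is weak: section 6 already reports the conduct of the trial in the past tense, so naming them now mainly documents what was done.

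Two stronger readings should be resisted. One is that omitting the strata biases the treatment effect or raises the false-positive rate. The error runs the other way: in these simulations the unadjusted test rejects too seldom whenever R² exceeds 0. The other is that the primary abstinence analysis, or the repeated-measures models in general, is impaired. Step 5 does not support that.

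**Conclusion.** The point holds in a narrow form. The stratification factors are not named and no listed model includes them. For the CSQ this leaves a valid but conservative comparison if the factors are prognostic: with 34 patients and an assumed R² of 0.1, 0.2 or 0.3, type I error is about 4, 3 or 2.5%, and the power forgone at an assumed 0.9 SD is roughly 3, 7 to 8 or 11 points. The loss is under one point at R² 0.03 and nil at R² 0. The cost is precision on one secondary outcome, so severity is minor. The figures depend on the assumed R² and effect size, on losses at random, and on stratification having taken place. The statement about the linear repeated-measures contrasts also assumes that stratum effects are constant over time.

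**What to change.** - **Section 7:** name the stratification factors and levels that the randomisation program used, or delete the word 'stratified' if none were used.
- **Section 5.3, after the CSQ sentence, if stratification was used:** *The CSQ regression includes the randomisation stratification factors as fixed main effects.*

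This takes one sentence in each place and no new data, since the factors are known at randomisation. The statistical cost is one degree of freedom per binary factor: about 0.1 power point for a single factor that proves not to be prognostic, and about 1 point if four strata are entered as three indicators. No change to the other models is needed on this ground.

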8 SAFETY MANAGEMENT

-Adverse Event Monitoring and Reporting

Any unanticipated problems, or adverse events, or new safety concerns will be promptly reported to the UNC IRB and discussed by the PIs and DSMG.

-See Protocol Synopsis "Data and Safety Monitoring Plan"

9 DATA COLLECTION AND MANAGEMENT

The DSMG will standardize data collection, management, and analysis, evaluate the progress of the study, and monitor participant safety and data quality. Privacy will be ensured for all participants in several ways. All potential participants will call the RC if interested in the study. Should potential

couples pass the telephone screening, they will be scheduled for an in-person interview, which will be conducted in a private room by one of the study personnel. During this interview, couples will be asked to complete measures pertaining to eating behavior and weight loss. They will be instructed that they are allowed to leave any answer blank if they do not want to complete the question. All participants and partners will be assigned a study number, which will be used in place of their name. The key linking study numbers to names will be kept in a locked filing cabinet and in a password protected excel file, only accessible to the PI. Participants will not be identified by name in any analysis or publication resulting from this study. Electronic files containing participant data will be password protected and stored on a secure server. Digital video and audio files of treatment sessions and assessments will be handled with extreme care, given that visual and audio information can identify participants. Audio and video recordings will be password protected, encrypted. The digital video recordings from the assessment sessions will be coded by trained research assistants who are well trained in the importance of participant confidentiality. Assessment sessions will be viewed only in confidential research settings where no one other than the coders, their trainers, and their supervisors can see the video monitor or hear the participants' voices. Recordings of assessment interviews and therapy sessions will be listened to and viewed only in confidential settings by the project staff supervising the therapists and assisting with treatment development, and the therapists themselves.

10 RECRUITMENT STRATEGY

Participants will be recruited from local physician offices, social media, advertisements, and local listservs. Potential participants will be asked to contact the study RC for more information. Potential participants will complete a screening questionnaire by phone with the RC, which will determine if they meet general study criteria.

11 CONSENT PROCESS

Patients responding to advertisements for participation will be asked by the RC if they are interested in hearing about the research study. Verbal consent must be obtained prior to obtaining any information about the participant other than contact information. After receiving information by phone and completing a phone consent screener in order to determine initial eligibility, they will be provided with written descriptions of the investigation, and the study will be explained in person by the RC before consenting. Participants will be provided an opportunity to have questions addressed by the PIs. Finally, participants will be required to sign a consent form approved by the IRB at UNC to participate in the proposed study. As detailed above, informed consent will be obtained by the research coordinator and not by a person with perceived authority, such as a treating physician.

12 PLANS FOR PUBLICATION

The primary outcome paper will include post-treatment, 3-month, and 6-month data on primary and secondary outcomes. Secondary papers will include coding of couple interactions and other secondary analysis results.

Van den Broucke, S., Vandereycken, W., & Vertommen, H. (1994). Psychological distress in husbands of eating disorder patients. *Am J Orthopsychiatry*, 64(2), 270-279.
http://www.ncbi.nlm.nih.gov/entrez/query.fcgi?cmd=Retrieve&db=PubMed&dopt=Citation&list_uids=8037235

Van den Broucke, S., Vandereycken, W., & Vertommen, H. (1995). Marital communication in eating disorder patients: a controlled observational study. *Int J Eat Disord*, 17(1), 1-21.
http://www.ncbi.nlm.nih.gov/entrez/query.fcgi?cmd=Retrieve&db=PubMed&dopt=Citation&list_uids=7894447

Van den Broucke, S., Vandereycken, W., & Vertommen, H. (1995). Marital intimacy in patients with an eating disorder: a controlled self-report study. *Br J Clin Psychol*, 34 (Pt 1), 67-78.
http://www.ncbi.nlm.nih.gov/entrez/query.fcgi?cmd=Retrieve&db=PubMed&dopt=Citation&list_uids=7757040

Whisman, M. A., Dementyeva, A., Baucom, D. H., & Bulik, C. M. (2012). Marital functioning and binge eating disorder in married women. *The International journal of eating disorders*, 45(3), 385-389. <https://doi.org/10.1002/eat.20935>

Table 1.**Comparison of Intervention Arms**

Table 1: Comparison of Intervention Arms		
Discipline	UNITE (16 sessions)	Individual CBT-E (16 sessions)
Medical	Psychiatrist (1)	Psychiatrist (1)
	Medical consults (as needed)	Medical consults (as needed)
Psycho-therapy	UNITE Couple Sessions (one 120-minute intro session, one 90-minute second session and fourteen 60 minute sessions) 1050 minutes	Individual CBT-E (one 120-minute intro session, one 90-minute second session and fourteen 60 minute sessions) 1050 minutes

Table 2.**UNITE Manual Components**

Table 2. UNITE Manual Components	
Session	Topic
Early Treatment	
1	Introduction to UNITE and Relationship Assessment
2	Understanding BED in a Couples Context: Symptoms and Course of Illness
3	BED Etiology, Treatment Goals, and Recovery
Mid-Treatment	
4-14	
Target 1: Communication around BED
 
 Emotional expressiveness communication skills 
Target 2: Problem-solving/Behavioral Change Skills
 
 Problem-solving communication skills Balanced eating Mealtimes, food purchasing and preparation 
Target 3: Partner-Assisted Emotion Regulation
 
 BED triggers and recovery cues Managing emotions effectively as a couple Effective self-care (i.e., physical activity, sleeping, relaxation) 
*Additional topics as needed:
 
 Body image, weight stigma Weight and health concerns Physical affection and sexuality *Flex session (incorporated anytime in treatment) *Flex session (incorporated anytime in treatment)
Late Treatment	
15	Relapse Prevention
16	Relapse Prevention and Termination
* Topics selected according to patient/couple needs	

Table 3.**Assessment Instruments and Schedule**

Table 3. Assessment Instruments and Schedule						
Assessment	Screen	Pre	Mid	Post	3 mo	6 mo
Phone Screen	1					
Background Info		1,2				
Eating Disorder Pathology						
EDE-Q		1	1	1	1	1
BES		1	1	1	1	1
YBOCS-BE		1	1	1		1
BE Frequency*		1	1	1	1	1
Height/Weight, Vitals		1,2	1,2	1,2	1,2	1,2
Mood/Psychological Functioning						
SCID		1,2				
BDI-II		1,2	1,2	1,2	1,2	1,2
BAI		1,2	1,2	1,2	1,2	1,2
DERS		1,2	1,2	1,2	1,2	1,2
DERS-Partner		1,2	1,2	1,2	1,2	1,2
Relationship Adjustment and Communication						
DAS*		1,2	1,2	1,2	1,2	1,2
MSI-R						
CPQ-SF		1,2	1,2	1,2	1,2	1,2
BISF		1,2	1,2	1,2	1,2	1,2
EDQOL		1	1	1	1	1
CTSR		1,2				
Videotaped Interactions		1,2		1,2	1,2	1,2
CSQ				1,2		
Therapist Feedback				3		

1 = Patient, 2 = Partner, 3 = UNITE Therapist

Pre = Pre-treatment, Mid = Mid-treatment, Post = Post-treatment, 3 mo = 3-month follow-up

*Binge eating and purging frequency, weekly
